ii. Whole body [¹¹C](R)-rolipram PET

Healthy controls will undergo PET scanning as outpatients, while MAS patients may be either inpatient or outpatient. Two intravenous catheters will be placed, one for radioligand injection and another to measure $[^{11}C](R)$ -rolipram concentrations. Total volume of blood sampling is about 30 mL.

PET scanning will be performed in the Clinical Center and will begin with a transmission scan by either CT or ⁶⁸Ge or ¹³⁷Cs source to correct for attenuation in the subsequent emission images. The PET radioligand [¹¹C](R)-rolipram (maximum activity of 20 mCi) will be injected intravenously over about one minute. The subject will be scanned over approximately two hours. Following the PET scan, the venous catheter will be removed.

If the brain or whole body PET scan is cancelled or incomplete for any reason eg, synthesis failure of $[^{11}C](R)$ -rolipram, camera issues, or other problems—and if the study participant did not receive any radioactive material, the scan will be repeated on the same or on another day as long as the participant is willing. The transmission scan may be repeated as well.

iii. Blocked Whole body scan $[^{11}C](R)$ -rolipram PET with roflumilast

Healthy controls will undergo PET scanning as outpatients, while MAS patients may be either inpatient or outpatient. Two intravenous catheters will be placed, one for radioligand injection and another to measure [¹¹C](R)-rolipram concentrations. Total volume of blood sampling is about 30 mL per scan.

PET scanning will be performed in the Clinical Center and will begin with a transmission scan by either CT or 68 Ge or 137 Cs source to correct for attenuation in the subsequent emission images. The PET radioligand [11 C](R)-rolipram (maximum activity of 20 mCi) will be injected intravenously over about one minute at the start of each scan. The subject will be scanned over approximately two hours. Subjects will be administered 500 µg roflumilast P.O. approximately 1-2 hours prior to [11 C](R)-rolipram administration. Because food consumption can affect the absorption of roflumilast, subjects will be asked to have a light breakfast (and light lunch if scan occurs in the afternoon) prior to the scan. Following the PET scan, the venous catheter will be removed.

iv. Brain MRI

All subjects, including those who receive only a whole body scan, will undergo a dedicated MRI of the brain for co-registration of PET images for analysis and to estimate brain morphology. Portions of the whole body PET scans image the brain. However, both volunteers and patients need not repeat the MRI scan if they had one of appropriate sequence within the prior year.

The MRI will be performed on a 3 Tesla magnet without the use of gadolinium contrast. Subjects will undergo safety screening prior to the MRI to rule out contraindications. The MRI will take place at the NIH Clinical Center and requires about

thirty to forty minutes. If subjects become anxious during a scan, lorazepam (0.5–1 mg) or another benzodiazepine may be administered orally, if not clinically contraindicated. Subjects can also request that the operator stop the scan at any time. Women of childbearing potential without a history of sterilization will be tested for pregnancy with a urine test prior to the MRI.

If the scan is cancelled or incomplete due to a problem with the scanner, the scan will be repeated on the same or on another day if the participant is willing.

v. Neuropsychiatric testing

Subjects with MAS will have the following examinations:

- 1. Wechsler Adult Intelligence Scale, Fourth Edition (WAIS-IV) or the Kaufman Brief Intelligence Test, Second Edition (KBIT-2) (17, 18)
- 2. Structured Clinical Interview for Non-Patient (SCID-NP) or SCID Patient Edition (SCID-P)
- 3. Edinburgh Handedness Inventory

Both the WAIS-IV and KBIT-2 provide an overall assessment of intelligence. SCID-NP characterizes neuropsychiatric symptoms. The Edinburgh Handedness Inventory assesses the dominance of a person's right or left hand. A decision to perform either the SCID-NP or SCID-P will be based on the patient's psychiatric history.

The WAIS-IV, KBIT-2, or the Edinburgh Handedness Inventory will not be repeated if the subject has already undergone these assessments under protocol 98-D-0145. The SCID-NP (or SCID-P) will not be repeated if performed within the past month.

e. End of participation

Study participation will end with the last PET or MRI scan the participant agreed to do. Patients will return for follow up under 98-D-0145. No follow up care will be needed for healthy volunteers.

5. Management of Data and Samples

a. Storage

Demographic and clinical data will be archived on a password-protected server. Imaging and blood data will be offloaded from the scanner/blood sampling device to a password-protected server. Clinical Safety Monitoring data will be archived together with other data. Laboratory test results will be stored on CRIS. Only study investigators will have access to stored data.

Blood samples for measurement of radioligand will be discarded after analysis, which will be performed on the day of the PET scan.

b. Data (*if applicable*: including genomic data) and sample sharing plan

Data may be shared. Data may be shared with collaborating laboratories at NIH or outside of NIH and/or submitted to NIH-designated repositories and databases if consent for sharing was obtained. Repositories receiving data from this protocol may be open-access or restricted access. Data will be stripped of identifiers and may be coded ("de-identified") or unlinked from an identifying code ("anonymized"). When coded data is shared, the key to the code will not be provided to collaborators, but will remain at NIH. Data may be shared with investigators and institutions with an FWA or operating under the Declaration of Helsinki (DoH) and reported at the time of continuing review. Sharing with investigators without an FWA or not operating under the DoH will be submitted for prospective IRB approval. Submissions to NIH-sponsored or supported databases and repositories will be reported at the time of continuing Review. Submission to non-NIH sponsored or supported databases and repositories will be submitted for prospective IRB approval.

Required approvals from the collaborating institution will be obtained and materials will be shipped in accordance with NIH and federal regulations.

6. Additional Considerations

a. Research with investigational drugs or devices

 $[^{11}C](R)$ -rolipram will be administered under IND #73,149, with [name] as the Sponsor and Investigator. The radioligand will be synthesized by the NIMH radiochemistry laboratory directed by [name].

Roflumilast is an FDA approved drug and meets the criteria of an IND exempt drug:

1. The drug product is lawfully marketed in the United States.

2. The investigation is not intended to be reported to FDA as a well-controlled study in support of a new indication and there is no intent to use it to support any other significant change in the labeling of the drug.

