Outcome measures: The primary outcome measure will be obtained in brain scans as the amount of radioligand binding quantified as distribution volume ($V_{\rm T}$). Calculated from both brain and plasma data, $V_{\rm T}$ reflects rolipram binding to PDE4, corrected for any individual differences in metabolism of the radioligand or regional blood flow in brain. The secondary outcome measure will be obtained in whole body scans as area under the curve (AUC) of radioactivity expressed as standard uptake value (SUV). SUV is calculated by normalizing radioactivity in PET images to injection activity and body weight. $V_{\rm T}$ in brain will be compared between subjects with MAS and healthy controls. AUC will be compared within-subjects with MAS between areas of craniofacial fibrous dysplasia and adjacent unaffected bone. AUC of whole body scans will also be compared between subjects with MAS and healthy controls. We hypothesize that subjects with MAS will show greater rolipram binding than healthy controls in brain regions, as well as greater rolipram uptake in bones affected by fibrous dysplasia than in unaffected bones. The third outcome measure will be the difference in SUV between the baseline whole body scan and the blocked (after roflumilast) whole body scan. This will help determine the amount of specific $[^{11}C](R)$ -rolipram binding in the periphery. We hypothesize that the $[^{11}C](R)$ -rolipram signal in the blocked scan will be greatly reduced, indicating that a majority of the signal in the baseline scan is specific

Table of Contents

1.	Introduction	6
2.	Study Objectives	10
3.	Subjects	11
4.	Study Design and Methods	12
5.	Management of Data and Samples	16
6.	Additional Considerations	17
7.	Risks and Discomforts	17
8.	Subject Safety Monitoring	19
9.	Outcome Measures	20
10.	Statistical Analysis	21
11.	Human Subjects Protection	21
12.	Anticipated Benefit	24
13.	Classification of Risk	24
14.	Consent Documents and Process	24
15.	Data and Safety Monitoring	25
16.	Quality Assurance	25
17.	Reporting of Unanticipated Problems, Adverse Events and Protocol Deviations	26
18.	Alternatives to Participation	26
19.	Privacy	26
20.	Confidentiality	26
21.	Conflict of Interest	27
22.	Technology Transfer	27
23.	Research and Travel Compensation	27
24.	References	29
25.	Attachments/ Appendices	31

List of Abbreviations

AUC	area under the curve
cAMP	3', 5'-cyclic adenosine monophosphate
MAS	McCune-Albright syndrome
MDD	major depressive disorder

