The purpose of this study is to assess whether uptake in dysplastic bone reflects parent radioligand binding to the enzyme or merely accumulation of radiometabolites, which are expected to have no affinity for the enzyme. For this purpose, we need not administer a receptor saturating dose of roflumilast, as the Lassen occupancy plot has great sensitivity to measure the percentage occupancy and then to extrapolate to 100% occupancy (Cunningham et al., *J. Cereb. Blood Flow & Metab.*, 30: 46-50, 2010). The sensitivity derives from the fact that it is a within subject comparison of multiple regions (in brain or periphery) at baseline and after blockade. We have used the Lassen plot numerous times, including to measure the occupancy of PDE4D subtype by the therapeutic candidate BPN14470. The figure below shows that that the occupancy (i.e., slope) is ~65% and the nondisplaceable uptake (V_{ND} or x-intercept) is ~4.9 mL \cdot cm⁻³.

2. Study Objectives

This study will investigate cAMP signaling in the brains of individuals with MAS using $[^{11}C](R)$ -rolipram PET imaging.

a. Primary objectives

We will study PDE4 levels in patients with MAS by comparing $[^{11}C](R)$ -rolipram binding in various brain regions between patients and age-matched healthy controls. In addition, in whole body imaging of patients with MAS, we will compare $[^{11}C](R)$ rolipram uptake between areas of fibrous dysplasia and adjacent unaffected bones. In whole body scans, we will also compare $[^{11}C](R)$ -rolipram uptake in peripheral organs between subjects with MAS and healthy controls. The reason for doing the latter comparison is that some tissues of MAS may contain the *GNAS* mutations even if there are no obvious structural changes.

b. Secondary objective

In order to quantify the amount of $[^{11}C](R)$ -rolipram binding in patient whole body scans, we will perform a blocking scan with 500 µg roflumilast, a FDA approved PDE4 inhibitor. Because of potential differences in metabolism of $[^{11}C](R)$ -rolipram in in the periphery of healthy controls and patients, it is difficult to interpret whether or not the $[^{11}C](R)$ -rolipram uptake is specific. By performing a blocking scan, we can quantify the amount of specific $[^{11}C](R)$ -rolipram binding to determine if there is a difference between healthy controls and patients.

3. Subjects

a. Description of study populations

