This study will have two populations: subjects with MAS and healthy control subjects. MAS subjects will be recruited from participants in 98-D-0145 "Screening and Natural History of Patients with Polyostotic Fibrous Dysplasia and the McCune-Albright

Syndrome" (PI: [name]). Participation in our protocol will not delay or interfere with the patient's treatment. For all patients, the diagnosis of MAS will have been made under 98-D-0145.

Healthy subjects will be recruited and screened by the Molecular Imaging Branch (MIB) under a separate protocol (01-M-0254 or 17-M-0181), and group-matched for age to the MAS subjects.

Our accrual number will be 20 for subjects with MAS and 15 for healthy controls. Assuming a withdrawal / dropout rate of \sim 20%, our target is to complete the study with 16 MAS subjects and 12 healthy controls. Both MAS and healthy subjects have one or two PET scans: one whole body and one brain scan. We expect that healthy subjects are more likely to have both brain and whole body scans and MAS subjects are less likely to do so. We expect \sim 10 brain and \sim 10 whole body scan to be performed in each group.

b. Inclusion criteria

Subjects with MAS

- **1.** At least 18 years of age
- 2. Able to provide self-consent
- 3. Diagnosed with MAS under 98-D-0145.
- 4. Have craniofacial fibrous dysplasia

Healthy Subjects

- 1. At least 18 years of age.
- 2. Healthy based on medical history and physical examination.

c. Exclusion criteria

Subjects with MAS

- 1. Serious medical conditions, which may interfere with study procedures. Such conditions include but not limited to significant bone abnormalities in wrist areas of both arms, which makes it difficult to place a radial arterial line, clinically marked dysfunction of liver or kidney, which may delay clearance of $[^{11}C](R)$ -rolipram.
- **2.** Clinically significant laboratory abnormalities not linked to endocrine abnormalities but that may interfere with the PET measurement or affect safety of the participant during this study.
- **3.** Positive HIV test.
- **4.** Head trauma resulting in a period of unconsciousness lasting longer than one hour.
- 5. Metallic foreign bodies that would be affected by the magnetic resonance imaging (MRI) magnet, or fear of enclosed spaces likely to make the subject unable to undergo an MRI scan.
- **6.** Recent research-related exposure to radiation (i.e., PET from other research) that, when combined with this study, would be above the allowable limits.

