All adverse events (AEs) will be recorded on the case report form. All AEs, including clinically significant abnormal findings on laboratory evaluations, regardless of severity, will be evaluated until satisfactory resolution. After removal of venous lines, the site of the catheter insertion will be carefully monitored for signs of bleeding.

Toxicity tables/criteria to be used

Toxicity will be assessed according to the NCI Common Terminology Criteria for Adverse Events (CTCAE) v.4.03 http://evs.nci.nih.gov/ftp1/CTCAE/About.html.

Criteria for individual subject withdrawal

We will stop study procedures for any subject with any Grade 2, Grade 3, or greater non-laboratory toxicity that is intolerable, persistent, or uncorrectable for more than several minutes. In addition, the Medical Advisory Investigator or a clinically credentialed investigator may terminate study procedures based on clinical judgments. Likely causes are pain at the site of catheter insertion and difficulties to stay in MRI and PET scanners, and the judgement of withdrawal by study investigators will be done as described above. In addition, study participants can voluntarily withdraw at any time for any reason.

9. Outcome Measures

a. Primary outcome measures

The primary outcome measure will be obtained in brain scans as the amount of radioligand binding quantified as distribution volume (V_T). Calculated from both brain and plasma data, V_T reflects the density of PDE4, corrected for any individual differences in metabolism of the radioligand or regional blood flow in brain.

b. Secondary outcome measures

The secondary outcome measure will be obtained in whole body scans as area under the curve (AUC) of radioactivity expressed as standard uptake value (SUV). SUVs are calculated by normalizing radioactivity in PET images to injection activity and body weight. Although AUC of SUV is not as fully quantitative as V_T , the AUC is widely used in clinical studies where arterial data are not obtained. If patients and healthy controls have markedly different clearance of $[^{11}C](R)$ -rolipram, group comparison using AUC of SUV may include errors. To correct group difference in clearance, in whole body imaging, venous concentrations of $[^{11}C](R)$ -rolipram will be measured at several time points. MRI measures of brain morphology including gray matter, white matter and CSF volume and folding will be estimated from the MRI images.

c. Tertiary outcome measure

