The third outcome measure will be the difference in SUV between the baseline and the blocked whole-body scans. SUV is calculated as stated above.

10. Statistical Analysis

a. Analysis of data/ study outcomes

PET and MRI images will be co-registered for anatomic definition of brain regions. Brain and plasma data will be analyzed with compartmental and graphical modeling to calculate $V_{\rm T}$, which is proportional to the density of receptor or enzyme. $V_{\rm T}$ will be calculated both for regions of the brain and on a voxel basis. PET whole body images will be analyzed by drawing organs and by calculating AUC of SUV. For comparisons between subjects with MAS and healthy controls in brain and peripheral organs, an unpaired test, such as t- and Mann-Whitney tests will be used. In addition, in peripheral organs of MAS, for comparisons of PET data between affected and unaffected organs, a paired test will be applied if the contralateral side is unaffected. If contralateral side is also affected or not available, an unpaired test will be applied to compare the same tissue/organ between patients and healthy controls. For the statistical analyses, SPSS, PMOD, SPM, Freesurfer or equivalent programs will be used.

b. Power analysis

This is an exploratory study focusing on PET imaging. Clinical data obtained under 98-D-0145 may be used to interpret the relationship between PET findings and clinical manifestations of the disease. Although constitutive activation of $G_s\alpha$ is expected to increase cAMP signaling, which increases PDE4 levels, PDE4 levels in MAS are not known in postmortem tissue either in brain or in peripheral organs such as bone. Therefore, we cannot do a realistic power calculation.

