To achieve the goals of this exploratory study, we request a total of 35 subjects: ~10 MAS subjects to undergo brain PET scan, ~10 MAS subjects to undergo whole body PET, and 15 healthy controls to undergo a brain scan and/or a whole body PET scan. By limiting subjects with MAS to those who have craniofacial fibrous dysplasia and neuropsychological symptoms, we expect to increase the likelihood of detecting changes in PET in this small sample size. To limit the number of study participants, all MAS and healthy subjects will be asked if they would be willing to have both brain and whole body PET scans. A smaller number of 15 healthy subjects are requested because healthy subjects are more likely to have both brain and whole body scans. Our previous study of [¹¹C](*R*)-rolipram brain scans in healthy subjects found that the coefficient of variation (SD/mean) of VT was 19%. Based on the activation of G_sa, we hypothesize that MAS patients will show increased rolipram binding for whichever one-sided test is appropriate. Assuming a 20% dropout from 10 subjects (thus, eight subjects per group) plus a 19% coefficient of variation (SD/mean) will provide a power of 0.80 to detect a 19% increase.

11. Human Subjects Protection

a. Subject selection

The study will be open to all racial and ethnic groups and will not target any particular group. Healthy volunteers will be recruited to match the patient group for age. Those who are HIV positive are excluded because the possible viral effects on the brain could interfere with interpretation of the outcome of the study.

b. Justification for exclusion of children

We will exclude children younger than 18 years of age to avoid radiation exposure to minors because the risks of radiation exposure outweighs the benefits.

c. Justification for inclusion of other vulnerable subjects

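### Tracer spill-in from craniofacial lesions can raise V_T in adjacent cortex in patients only, and Section 10a has no step to detect or remove it

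*Combined protocol and SAP*

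**What the plan says.** - **Who is enrolled.** Inclusion criterion 4 for MAS subjects (Section 3b) is "Have craniofacial fibrous dysplasia". The criteria for healthy subjects have no counterpart. Section 10b gives the restriction as a way to improve the chance of detecting PET changes: "By limiting subjects with MAS to those who have craniofacial fibrous dysplasia".
- **What the lesions are expected to do.** The Précis (Outcome measures) predicts "greater rolipram uptake in bones affected by fibrous dysplasia than in unaffected bones", without giving a size. The roflumilast part of Section 1 leaves the source of that signal open; the blocked scan is meant to "assess whether uptake in dysplastic bone reflects parent radioligand binding to the enzyme or merely accumulation of radiometabolites".
- **What the primary comparison is.** Section 9a: "The primary outcome measure will be obtained in brain scans as the amount of radioligand binding quantified as distribution volume". The Précis states the direction: "We hypothesize that subjects with MAS will show greater rolipram binding than healthy controls in brain regions". Section 10b intends a one-sided test.
- **How the brain images are analysed.** Section 10a co-registers PET with MRI and models brain and plasma data. It says that V_T "will be calculated both for regions of the brain and on a voxel basis", and then applies an unpaired test. Sections 4.d.iv and 9b use the MRI for co-registration and brain morphology. Neither section mentions partial-volume or spill-in correction, lesion masking, or separate reporting of cortex near lesions and away from them.

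**The concern.** A PET image is blurred, so activity just outside the brain is partly counted inside it. Every scanned head has skull next to cortex, and spill-in from normal skull is roughly common to both groups. Extra signal from dysplastic bone is not: it can occur only in patients, and it pushes V_T upward, as the primary hypothesis does. The lesion does not have to be hotter than cortex. It only has to be hotter than the skull at the same place in a control.

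The arterial input function corrects for tracer metabolism and delivery, not for signal from neighbouring tissue. If the bone signal is partly radiometabolite, a model driven by parent tracer in plasma would still read the spilled-in part as tissue uptake of parent. The blocked scan does not settle this for the brain, because it is a whole-body scan and optional.

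At stake is how a positive finding in cortex beside a lesion would be read. Without a rule set in advance, a rise there could be reported as raised brain PDE4 when it reflects uptake in bone.

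**Working it through.** **Figures from the plan (Section 10b).** Eight subjects per group after dropout, coefficient of variation 19%, target increase 19%, stated power 0.80, one-sided test. Alpha is not given; I assume 0.05. A two-sample t test with these inputs gives power 0.60 (0.64 by the normal approximation), so 0.80 does not reproduce. That is a separate matter. Here the 19% serves only as a yardstick.

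**Assumed inputs, none of them in the documents.** Gaussian blur with FWHM of 4, 6 or 8 mm; a lesion 15 mm thick and wide enough to be treated as a slab; a cortical strip 3 mm thick at gap d from the lesion; lesion activity above control skull equal to c times cortical activity, with c from 0.1 to 1.5. A proportional rise in regional activity is taken as the same proportional rise in V_T.

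**Formula.** With s = FWHM/2.355, the spill-in fraction is f = the mean, over x from d to d + 3 mm, of Φ(−x/s) − Φ(−(x + 15)/s). The false rise in V_T is 100 × f × c per cent.

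| FWHM | gap d | f | rise at c = 0.1 | rise at c = 1.5 |
|---|---|---|---|---|
| 4 mm | 1 mm | 0.096 | 1.0% | 14% |
| 4 mm | 3 mm | 0.009 | 0.1% | 1.3% |
| 6 mm | 1 mm | 0.177 | 1.8% | 27% |
| 6 mm | 3 mm | 0.047 | 0.5% | 7% |
| 6 mm | 5 mm | 0.008 | 0.1% | 1.2% |
| 8 mm | 1 mm | 0.238 | 2.4% | 36% |
| 8 mm | 3 mm | 0.100 | 1.0% | 15% |
| 8 mm | 5 mm | 0.032 | 0.3% | 4.8% |

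**Larger region.** Averaging over 20 mm of depth from a 1 mm gap at FWHM 6 mm gives f = 0.030, so the rise is 100 × 0.030 × 0.1 = 0.3% to 100 × 0.030 × 1.5 = 4.5%.

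**Differing lesion sites.** The group-mean rise at a location is the rise in an affected patient times the share of patients with a lesion there. If, for illustration, 3 of 8 share a site, 1.8-27% becomes 0.7-10% (multiply by 3/8). Differing sites also widen the spread within the patient group.

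**Effect on the test.** Suppose there is no true difference, and all eight patients carry the same bias in a region. The one-sided false-positive rate there rises from 0.050 to 0.074 at a 2% bias, 0.126 at 5% and 0.26 at 10%. These are upper figures for a given bias in affected patients, because not all patients need be affected.

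**How wide a mask is needed.** The same formula with d equal to one FWHM gives f = 0.0026 at 6 mm and 0.0033 at 8 mm. Even at c = 1.5 that leaves a rise of about 0.4% (100 × 0.0026 × 1.5) and 0.5% (100 × 0.0033 × 1.5). Beyond one and a half FWHM the remainder is negligible.

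**The case against.** The best case against acting has four parts.

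1. **Not every patient is exposed.** A reader might infer that the criterion puts a lesion beside the brain in every patient. It does not. It asks for craniofacial disease, which may be confined to the face, and Section 1 describes lesions as varying in site. The exposed share is unknown. This stands.
2. **The size is assumed.** A reader might infer from the upper figures that spill-in could produce the whole 19% target. Under the model this needs a gap of about 1 mm, the upper part of the assumed uptake range and a resolution of 6 mm or worse. It also needs most patients to share a site. The documents predict only that lesions exceed unaffected bone; they say nothing of lesion against cortex. In a deep or large region the effect is a few per cent at most. This stands too.
3. **Location is visible.** A reader might infer that brain and bone findings could not be told apart. Regional and voxel maps partly show the pattern: a rise in deep structures as well as cortex would argue against spill-in. But Section 2a names no particular regions and no interpretation rule is set, so a rise confined to cortex beside a lesion could still be counted as support.
4. **The study is exploratory and the images can be reprocessed later.** That is true, and nothing is lost irrecoverably. It does not remove the benefit of fixing the mask and the reading rule before results are seen.

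Moving the primary comparison out of cortex altogether would go too far, given the study's interest in a neuropsychiatric phenotype.

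**Conclusion.** The concern holds in a limited form. The plan requires lesions in one group, expects them to take up more tracer, tests for a rise in brain V_T in the same direction, and has no step to detect or remove spill-in. In patients whose lesions abut the cranial cavity, V_T in the nearest cortex can therefore be biased upward.

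The bias is local. At FWHM 6 mm and a lesion excess of 0.1 to 1.5 times cortical activity, it runs from about 2-27% in a thin strip 1 mm away to about 1% or less at 5 mm, and about 0.3-4.5% in a region 20 mm deep. Group means are smaller when sites differ. Resolution, lesion geometry, uptake ratio and the share of exposed patients are all assumptions, so these ranges show what is possible and do not estimate what will occur. The documents do not support saying that the primary comparison is invalid or that a global rise in V_T could be explained this way. This is a cheap improvement to the analysis, not a defect in the design.

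**What to change.** In Section 10a:

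1. Keep the planned regional and voxel comparison of V_T.
2. Add a prespecified comparison that excludes voxels within about one to one and a half scanner FWHM of any craniofacial lesion seen on the study MRI, or on the transmission CT where CT is used. Apply the same mask to controls. State the scanner FWHM and how individual patients' masks are combined.
3. Report regions remote from the skull, such as striatum and thalamus, alongside it.
4. State in advance that a rise confined to lesion-adjacent cortex will not be taken as evidence of raised brain PDE4.

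The cost is a paragraph of text and some image processing. Section 4.d.iv already calls for a brain MRI in all subjects, so no new scan is needed. The downside is that some cortical voxels are lost from the masked analysis, more of them if lesion sites vary widely between patients; the unmasked comparison remains in place.
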